3.5.3 Presentation of results

Number of administrations and number of [REDACTED] doses will be summarized using descriptive statistics. Analysis on NCPD is described in the efficacy section 4.1.2.2.

Number of days and proportion of days with prednisone equivalent dose ≤ 10 mg are analysed in the same way as NCPD, except for the subgroup analyses where only results will be presented for the disease type subgroup.

All study drug administration data will be listed. Also a detailed listing of prednisone administration and NCPD will be provided including prednisone equivalent doses with body weight at intake, dates of ICE, CR, CRmin and EoS.

Frequency tabulations with percentages will be produced for:

- Number of participants/caregivers receiving the self-administration training (denominator is all participants in SAF)
- Number of training visits received (denominator is number of participants/caregivers receiving training)
- Number of participants/caregivers who were adequately trained and capable to self-administer efgartigimod (denominator is number of participants/caregivers receiving training)
- Number of training visits before being considered capable to self-administer (denominator is number of participants/caregivers receiving training)
- Number of administrations by administrator and location (at home/on-site) per visit and overall

Tables to be produced for the topline results (see list of output in 8.1) will be presented for all participants (PV+PF) as well as for PV participants. Tables on IMP administration will also be presented for PF participants separately.

Line plots for the mean daily prednisone dose (mg) and mean cumulative prednisone dose (g) over time will be produced for all participants (PV+PF) as well as for PV participants. These plots will be produced under the following approaches for handling missing data:

- a) complete case analysis;
- b) last observation carried forward;
- c) baseline observation carried forward.

	Statistical Analysis Plan	
ARGX-113-1904	Final analysis	Final 2.0 of 22NOV2023

4. EFFICACY, PHARMACOKINETIC, PHARMACODYNAMIC AND IMMUNOGENICITY ANALYSES

4.1 EFFICACY AND QUALITY OF LIFE

4.1.1 Available data

Efficacy will be evaluated by assessments of PDAI, DC, EoC, CR, CRmin, complete remission off prednisone therapy (CROff), cumulative prednisone dose, flares and treatment failure. Quality of life will be measured using Autoimmune Bullous Disease Quality of life (ABQOL) Questionnaire and EuroQoL 5-Dimension 5-Levels- (EQ-5D-5L) Scale. The health impact of glucocorticoid (GC) use will be measured using the Glucocorticoid Toxicity Index (GTI) (see section 9.3).

4.1.2 Endpoints and derivation rules

The analysis of primary and key secondary endpoints will be repeated on the PP set. In addition, these analyses will also be repeated on the mITT population excluding data impacted by the conflict in Ukraine, i.e. excluding participants from Ukraine that have not completed the study by the onset of conflict (24Feb2022). All the above repetitions will be performed on the primary estimand only.

For all references to weeks, analysis visits are considered as described in section 2.2.4 unless specified otherwise. If multiple assessments fall within the same analysis window, only the assessment closest to the target date will be considered unless specified otherwise. Other assessments within this window will only be listed and not considered in the below analyses. Only the time to response endpoint (see section 4.1.2.2) will be derived using all possible measurements and not only the one closest to the target of the analysis visit. Visits during the treatment and FU phase will be considered defining the different responses, unless mentioned otherwise.

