Visit Window	±0 days	±2 days ^f		V1 + 7 × ±2 days ^f			±2 days ^f		±3 days ^f
Disease assessment ^{hh}		X	X		X	X	X	X	X
Prednisone taper ⁱⁱ			X	X	X	X	X	X	X
AE monitoring	Continuous monitoring								

ABQOL=Autoimmune Bullous Disease Quality of Life; admin=administration; BL=baseline; BMI=body mass index; CR=complete clinical remission; CRmin=CR on minimal therapy; D=day; DC=disease control; DIF=direct immunofluorescence; Dsg=desmoglein; ECG=electrocardiogram; ED=early discontinuation; EoC=end of consolidation; EoS=end of study; FSH=follicle-stimulating hormone; GTI=Glucocorticoid Toxicity Index; HLA=human leukocyte antigen; IgG=immunoglobulin G; ICF=informed consent form; IMP=investigational medicinal product; OLE=open-label extension; PDAI=Pemphigus Disease Area Index; PK=pharmacokinetics; RBC=red blood cells; UNS=unscheduled visit; WBC=white blood cells; W=week; V=visit

^a All participants will complete EoS/ED, which will be the end of the trial for participants who enroll in the OLE trial ARGX-113-1905. Participants who do not enroll in the OLE trial ARGX 113 1905 will complete the follow-up visits at W34 and W38.

^b In case of suspected new lesions as reported by the participants, AEs, flare or other safety reasons, participants should come to the clinic. This may require an unscheduled visit. Depending on the reason for the visit, different assessments need to be performed. See Section 8 for more information. Participants with new lesions or flare after achieving CR should return to weekly on-site visits until CR is achieved again.

^c A minimum of 6 on-site visits, V1(BL)/W1 to W6, are required before switching to home administrations, even if CR is achieved earlier than W6. The W7 visit is the first eligible “IMP administration only” visit (refer to column “Weekly home or on-site visits until CRmin”), at home or on-site, if CR is achieved between W1 and W6.

^d Home visits are allowed once participants achieve CR, but not before W7. The investigator should call the participant every 2 weeks until CRmin is achieved to confirm the participant is still in CR. On-site visits may continue at the investigator’s discretion.

^e W38 (follow-up visit 2) is the end of the trial for participants who do not enroll in the OLE trial ARGX-113-1905. The W38 follow-up visit will only be required for those participants who were still receiving IMP at least once from W27 onward. For participants who ended treatment prior to W27, W34 will be the end of the trial.

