In case of flare in the period between DC and CRmin, the prednisone dose will be increased. A flare is defined by the appearance of 3 or more new lesions in a 4-week period that do not heal spontaneously within 1 week, or by the extension of established lesions in a participant who had achieved DC. If the flare occurs after CR and IMP was administered at home by a nurse, the participant will resume weekly on-site visits until he/she achieves CR again. Participants who are not controlled by a prednisone dose that is 2 dose levels above the dose at which the flare between DC and CRmin is observed and that is at least 0.3 mg/kg/day (eg, according to [Table 3](#)) will be considered treatment failures. At visits when at least 1 new lesion is observed or established lesions remain extensive without being defined as a flare, the prednisone dose will be maintained or may be increased, according to clinical judgment. If the lesion resolves, tapering of the prednisone dose will be pursued as planned.

Participants who experience treatment failure, or flare after achieving CRmin, will be allowed to roll over into the OLE trial ARGX-113-1905 earlier than W31. Participants who do not roll over into the OLE trial ARGX-113-1905 will complete the treatment-free follow-up period. Participants experiencing an SAE related to prednisone may also benefit from an early roll over to the OLE trial, according to clinical judgment.

Trial procedures will be performed per the SoA as detailed in [Section 1.3](#).

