4.4. End of Study Definition

The end of the study is defined as the date of the last visit of the last participant in the study.

A participant is considered to have completed the study if he/she has completed all periods of the study including the end of study (EoS)/early discontinuation (ED) visit and any follow-up visits, if applicable, depending on whether the participant rolls over to ARGX-113-1905 or continues the treatment-free follow-up period in ARGX-113-1904.

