Assessment ^a	UNS – any reason other than new lesion(s) or flare	UNS – new lesion(s)	UNS – flare
Physical examination & vital signs	X	X ^b	X ^b
PDAI	X	X	X
Disease assessment	X	X	X
Urinalysis	X		
Urine pregnancy	X		
Blood sample for PK	Only if IMP is administered	Only if IMP is administered	Only if IMP is administered

Assessment ^a	UNS – any reason other than new lesion(s) or flare	UNS – new lesion(s)	UNS – flare
Clinical chemistry & hematology	At the discretion of the investigator	At the discretion of the investigator	At the discretion of the investigator
Anti-Dsg-1 and anti-Dsg-3 antibodies			X ^b
Vaccination antibodies ^c			X ^b
Total IgG (no IgG subtypes)	X		
IgG autoantibody subtypes and cytokines ^c			X ^b
Photography ^c (substudy conducted at selected sites)	At the discretion of the investigator	At the discretion of the investigator	At the discretion of the investigator
IMP administration	Only if the UNS coincides with a planned IMP-only visit	Only if the UNS coincides with a planned IMP-only visit	Only if the UNS coincides with a planned IMP-only visit
Prednisone taper	X	X	X
AE monitoring	X	X	X
Concomitant therapies	X	X	X

IgG=immunoglobulin gamma; IMP=investigational medicinal product; PDAI=Pemphigus Disease Area Index; UNS=unscheduled visit

^a These assessments can coincide with a planned observational or IMP-only visit.

^b These assessments should be performed once (only during the visit where the new lesion(s) or flare is confirmed. They should not be repeated at subsequent visits (even if more new lesions develop at these subsequent visits or the flare is sustained) unless the subsequent visits coincide with planned observational or IMP-only visits and the assessment is to be performed during those visits per the SoA.

^c These assessments will not be performed in China.

Treatment-free Follow-up Period

Participants who reach week 31, discontinue early, or participants under treatment failure, and who do not roll over to the OLE trial, will enter the treatment-free follow-up period. There is a permissible visit window of ±3 days during the follow-up period.

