Participants who experience treatment failure, or flare after achieving CRmin, will be allowed to roll over into the OLE study ARGX-113-1905 earlier than week 30. Participants who do not roll over into study ARGX-113-1905 will complete an 8-week treatment-free follow-up period. Participants experiencing an SAE related to prednisone in ARGX-113-1904 are considered treatment failures and may also benefit from an early roll over to the OLE, according to clinical judgment of the investigators.

	Statistical Analysis Plan	
ARGX-113-1904	Final analysis	Final 2.0 of 22NOV2023

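### The Ukraine-excluded repeat analysis selects participants by study completion, a post-randomisation status that depends on outcome; a first-dose date would not

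*SAP*

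**What the plan says.** SAP 4.1.2 plans a repeat of the primary and key secondary analyses on mITT, "excluding participants from Ukraine that have not completed the study by the onset of conflict (24Feb2022". The repeat is supportive: "All the above repetitions will be performed on the primary estimand only". The section does not say what completed means.

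The only definition is in Protocol 4.4, where a participant has completed the study once he or she "has completed all periods of the study including the end of study (EoS)/early discontinuation (ED) visit", plus follow-up visits where these apply. Footnote a of the schedule of activities (Protocol 1.3) adds: "All participants will complete EoS/ED, which will be the end of the trial for participants who enroll in the OLE trial ARGX-113-1905".

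Protocol 4.1 permits early exit: "Participants who experience treatment failure, or flare after achieving CRmin, will be allowed to roll over into the OLE trial ARGX-113-1905 earlier than W31". SAP 1.2 agrees ("will be allowed to roll over into the OLE study ARGX-113-1905 earlier than week 30"), and Protocol 4.2 says that failures at the top prednisone step are invited to enter the extension early. Under Protocol 8, failures "who do not roll over to the OLE trial, will enter the treatment-free follow-up period", so they are not complete at the ED visit.

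SAP 3.1.1 tabulates completed and discontinued as separate categories taken from the study termination page. SAP 4.1.2.1 counts any CRmin up to day 218 as a response and treats a CRmin that was never recorded as non-response.

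**The concern.** A set meant to remove data touched by an outside event should be defined by something fixed before outcome, such as place and date of entry. Here membership turns on whether the participant had finished. Participants whose 218-day window spans 24Feb2022 could finish before that date mainly by leaving early, and the main reason for leaving early is treatment failure. Two Ukrainian participants dosed on the same day in autumn 2021 can therefore be treated differently because one had failed and the other had not.

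At stake is whether the repeat answers its own question. If it differs from the main result, part of the difference could come from this selection and not from the conflict.

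**Working it through.** **1. The plan's own figure.** The exclusion rule carries no number. The one planning figure tied to the conflict is in Protocol 9.3: 95% power with 183 PV participants at 34% against 11%, 2:1, two-sided 5%, for the additional off-IMP analysis.
- Pooled rate: (0.11 + 2×0.34)/3 = 0.2633.
- Null SE: √[0.2633×0.7367×(1/61 + 1/122)] = 0.0691.
- Alternative SE: √[0.11×0.89/61 + 0.34×0.66/122] = 0.0587.
- z = (0.23 − 1.96×0.0691)/0.0587 = 1.61, so power is 94.7%, with no participants lost. The figure reproduces.

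**2. Dates.** Day 218 is first dose + 217 days, and 24Feb2022 − 217 days = 22Jul2021. Anyone first dosed on or after 22Jul2021 reaches day 218 on or after the onset. W31 has target day 211 (SAP 2.2.4), and 24Feb2022 − 210 days = 29Jul2021. Adding the seven weeks to the last follow-up visit gives 10Jun2021. So a participant first dosed between 11Jun2021 and 21Jul2021 who did not roll over can be dropped for being in follow-up although day 218 had already passed.

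**3. Who is kept.** Ukrainian participants first dosed in the 218 days before the onset:

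| Status | Early rollover counts as completed | Early exit recorded as discontinued |
|---|---|---|
| Failed and rolled over before onset | Kept, mostly non-responder | Dropped |
| Flare after CRmin, rolled over before onset | Kept, responder | Dropped |
| Still on treatment at onset | Dropped | Dropped |
| In CRmin, awaiting W31 | Dropped | Dropped |
| In follow-up | Dropped | Dropped |
| Failed on or after 24Feb2022 | Dropped | Dropped |

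Under the second reading the selection moves to earlier entrants. A Ukrainian participant who failed and left long before the conflict is dropped, while one of the same entry date who stayed to the end is kept.

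**4. Size under the first reading.** From Protocol 9.3: 183 PV participants at 2:1 (122/61) and planning rates of 50% and 20%. Assumed, because the documents give no figures: u straddling PV participants (9 to 36, at 2:1), entry uniform over the 31 weeks before the onset, early-failure rates fE and fP, and exit by rollover uniform over weeks 3 to 30. All kept failures are taken as non-responders.

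Probability that an early failure exits before the onset: k = [(30 − 3)/2 + 1]/31 = 14.5/31 = 0.468.

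Active rate = 0.50(122 − 2u/3) / [122 − 2u/3 + (2u/3)·fE·k]; placebo rate = 0.20(61 − u/3) / [61 − u/3 + (u/3)·fP·k].

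Example, u = 36, 10%/10%: active 49/(98 + 1.12) = 49.4%; placebo 9.8/(49 + 0.56) = 19.8%; difference 29.7 points before rounding the rates.

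| u | fE / fP | Failures kept (active, placebo) | Rates | Difference (points) |
|---|---|---|---|---|
| 9 | 10% / 10% | 0.28, 0.14 | 49.9% / 20.0% | 29.9 |
| 9 | 10% / 30% | 0.28, 0.42 | 49.9% / 19.9% | 30.0 |
| 9 | 20% / 40% | 0.56, 0.56 | 49.8% / 19.8% | 30.0 |
| 36 | 10% / 10% | 1.12, 0.56 | 49.4% / 19.8% | 29.7 |
| 36 | 10% / 30% | 1.12, 1.68 | 49.4% / 19.3% | 30.1 |
| 36 | 20% / 40% | 2.25, 2.25 | 48.9% / 19.1% | 29.8 |

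**5. Direction.** To first order the change in the difference is −x·k·(0.5·fE − 0.2·fP), where x = u/(183 − u). It is positive only if fP exceeds 2.5 times fE. A wider gap shows this: with u = 45, rates of 15%/50%, entry over 218 days and exits on days 40 to 210, k = (85 + 8)/218 = 0.427. Active is 46/(92 + 1.92) = 48.98%, placebo is 9.2/(46 + 3.20) = 18.70%, and the difference is 30.3. Pairings further from the 2.5 ratio than those shown would move the result more.

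**The case against.** The best defence is that completion must precede the onset, so every Ukrainian outcome kept was observed before the war. That is right. A reader might infer that the rule keeps failures that occurred during the conflict; it does not, because those participants had not completed by the cut-off. Nor does it touch participants outside Ukraine.

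Second, counting an early rollover as completion is one reading. The SAP leaves the term undefined and its disposition table separates completed from discontinued. Rollover is also permitted and not required, and failures who stay out of the extension must finish follow-up first. These points narrow the first reading, but they do not rescue the rule, since the other reading selects on outcome in the opposite direction.

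Third, a reader might infer that every straddling participant kept is a failure. Flare after CRmin also allows early exit, and those participants are responders. Someone dosed in the few days after 22Jul2021 could reach W31 normally before the onset.

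Fourth, it is tempting to say that the rule favours efgartigimod because placebo participants fail more often. The documents give no early-failure rates, and the sign changes within plausible assumptions.

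Fifth, this is not the only view of the result without Ukrainian data. SAP 4.1.5 has subgroups by region, and SAP 3.2.2 places Ukraine in Rest of World, so the other three regional estimates contain none.

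Finally, a date rule discards some outcomes fully observed before the conflict. That is true and is its price.

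**Conclusion.** The point holds as a minor flaw in a supportive analysis. The Ukraine-excluded set is conditioned on a post-randomisation status that depends on outcome under either reading of completed, and the reading decides which way the selection runs.

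For the first reading, the difference shifts by about 0.3 points or less against 30.0 in the pairings shown, and the direction is uncertain. That rests on assumed numbers of straddling participants, entry pattern, early-failure rates and exit times. The second reading was not sized; it would need the number of Ukrainian participants who entered before 22Jul2021, which is also not given. The alpha-controlled primary test uses the full mITT PV set and is unaffected.

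**What to change.** In SAP 4.1.2, define the set by a baseline date: exclude every Ukrainian participant whose first IMP administration was on or after 22Jul2021, regardless of completion, rollover, discontinuation or outcome. Day 218 then falls before 24Feb2022 for every Ukrainian participant who remains. That window also suits the key secondary endpoints, whose periods run to day 218. The rule needs no definition of completed, and it keeps participants who were in follow-up at the onset but whose day 218 had already passed.

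The cost is one line of text and the loss, from this repeat only, of a few participants whose outcome was fully observed before the conflict. In the illustration these are 0.4 to 4.5 early failures (0.28 + 0.14 to 2.25 + 2.25). The PV set becomes 174 to 147 (183 − 9 to 183 − 36), with an expected difference of 30.0 points. If the completion-based set is kept as well, the SAP should state whether early rollover counts as completion.

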During the IMP treatment period, all assessments and procedures have to be performed before the start of the IMP administration, except for the continuous assessment of AEs (see Section 8.4), and the recording of concomitant therapy and procedures (see Section 8.3.5).

At all visits, the efficacy and QoL assessments should be performed first, prior to any other trial-specific procedure with the only exception of obtaining informed consent at screening. The EQ-5D-5L and ABQOL should be performed prior to all other efficacy assessments (Section 8.2).

End of Study (EoS)/Early Discontinuation (ED)

All participants will complete W31/ED, which will be EoS for participants who enroll in the OLE trial ARGX-113-1905.

Unscheduled Visits

In case of suspected new lesions as reported by the participant, AEs, flare, or other safety reasons, participants should come to the clinic. This may require an unscheduled visit or can coincide with a planned observational or IMP-only visit. At this visit, assessments need to be performed as follows:

- Assessments as specified in [Table 4](#) below:

Note: In case of new lesions or flare, the assessments indicated with footnote “b” in [Table 4](#) should be performed only once at the visit where the new lesions or the flare is confirmed. These should not be repeated at subsequent visits (even if more new lesions develop at these subsequent visits or the flare is sustained) unless the subsequent visits coincide with planned observational or IMP-only visits and the assessments are to be performed during those visits per the SoA .

- Assessments specified for the planned observational or IMP-only visit per the SoA (Section 1.3), if applicable.

In case the participant was in CR when the new lesions/flare was observed: the planned weekly IMP-only or observational visits should be performed on-site (home visits are not allowed) for disease assessment and PDAI until CR is reached again.

In case the participant was in CRmin or CROff at the time of the new lesions: the participant should return for weekly on-site visits for disease assessment and PDAI until CR is reached again. This will require unscheduled visits or can coincide with planned observational visits. In case flare is confirmed in participants who had achieved CRmin, participants will be allowed to roll over into the OLE trial ARGX-113-1905 earlier than week 31.

Table 4: Assessments to be Performed During an Unscheduled Visit

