2.2.4 Analysis visits

All assessments, including unscheduled assessments, will be allocated to analysis windows as defined below. Tables and listings will present the analysis windows, not the case report form (CRF) visits. Allocation of assessments will be done using their relative day (ADYP, see section 2.2.3). Visit windows are the mid-point between the scheduled study days for each visit.

Table 3: Analysis visits

Following analysis visits are allocated based on ADYP using start of phase as reference day.

Phase	Analysis window	Target ADYP	Lower limit ADYP	Upper limit ADYP
Screening	Screening	-21	-INF	1
Treatment	Baseline	1	-INF	1 ^[1]
	Week 1	8	1 ^[1]	11
	Week 2	15	12	18
	Week 3	22	19	25
	Week (3+ x ^[2])	22 + (x ^[2] *7 days)	19 + (x ^[2] *7 days)	25 + (x ^[2] *7 days)

	Week 29	204	201	207
	Week 30	211	208	End day of treatment phase
Follow-up	FU Week 3	21	1	35
	FU Week 7	49	36	End of follow-up phase

^[1] An assessment on Day 1 will be attributed to Baseline in case it is before the first IMP administration, to Week 1 otherwise.

^[2] x=1,...,25

	Statistical Analysis Plan	
ARGX-113-1904	Final analysis	Final 2.0 of 22NOV2023

Table 4: Additional analysis visits for PD, Albumin, LDL-C and PDAI

Additionally following analysis visits are allocated based on ADYP using start of period as reference day.

Phase	Period	Analysis window	Target ADYP	Lower limit ADYP	Upper limit ADYP
Treatment	On treatment	Baseline	1	-INF	1 ^[1]
		Week 1	8	1 ^[1]	11
		Week 2	15	12	18
		Week 3	22	19	25
		Week (3+ x ^[2])	22 + (x ^[2] *7 days)	19 + (x ^[2] *7 days)	25 + (x ^[2] *7 days)
	
		Week 30	211	208	Last IMP administration date
	Off treatment	Week 1	8	1	11
		Week 2	15	12	18
		Week 3	22	19	25
		Week (3+ x ^[2])	22 + (x ^[2] *7 days)	19 + (x ^[2] *7 days)	25 + (x ^[2] *7 days)
	
		Week 30	211	208	End day of treatment phase

^[1] An assessment on Day 1 will be attributed to Baseline in case it is before the first IMP administration, to Week 1 otherwise.

^[2] x=1,...,26

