4.1.2.1 PRIMARY ENDPOINT

The primary endpoint is the proportion of PV participants having achieved CRmin (as assessed by the investigator) within 30 weeks. A stratified Cochran-Mantel-Haenszel (CMH) test will be calculated with the stratification factors of disease status, disease severity, and body weight at randomization.

Disease activity relative day will be calculated as specified in Section 2.2.3. Any CRmin achieved with a relative day up to day 218 is counted as a primary endpoint response. CRmin cases achieved for the first time after day 218 will not be considered.

The main analysis on the primary endpoint will use the ‘composite strategy’ approach in case of main intercurrent events. This strategy implies that when a main intercurrent event (ICE) occurs, a participant is considered a non-responder. This happens in the following situations:

	Statistical Analysis Plan	
ARGX-113-1904	Final analysis	Final 2.0 of 22NOV2023

- Intercurrent medications (see section 3.4.2) before CRmin
 - Immunosuppressants or dapsone at therapeutic doses for at least 4 weeks in total in the last 12 weeks before achieving CRmin
 - IVIg/SCIg at immunomodulating dose (≥ 1 g/kg/month) before achieving CRmin
 - Immunoabsorption or plasma exchange (at least 1 procedure) before achieving CRmin
 - Rituximab or other anti-CD20 biologics (at least 1 infusion) before achieving CRmin
 - IV or IM corticosteroids administered (at least 1 administration, any dose) once the participant has achieved minimal prednisone (or prednisone equivalent) dose of ≤ 10 mg/day (i.e., during the 8 week period required in the protocol to confirm the CRmin status) or administered at any moment before achieving CRmin in any of the three following situations:
 - a) more than 60 mg for 3 consecutive days
 - b) more than 40 mg for 4 consecutive days
 - c) more than 7 days in total
 - Tetracyclines administered at least 100 mg/day for at least 2 weeks in total in the last 10 weeks before achieving CRmin
 - Any interventional study drug under development for pemphigus given before achieving CRmin
- Discontinuation of IMP before CRmin due to lack of efficacy
- Death

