4.1.2.3 OTHER SECONDARY ENDPOINTS (NOT ALPHA CONTROLLED)

All other secondary endpoints will be analyzed using the mITT population. Analyses related to data in the period after an event (CRmin, DC) can only be performed in participants with that event.

1. Proportion of PF participants who achieve CRmin within 30 weeks: same derivation as for the primary endpoint (composite strategy) but then for PF participants.
2. Time to CRmin in PV, PF and all participants: same derivation as third key secondary endpoint (composite strategy) but using date of achieving CRmin. Time to CRmin is defined as the time to the moment that the participant achieves CRmin status defined as complete remission while receiving prednisone therapy at 10 mg/day or less for at least 8 weeks, based on the assessment of the investigator. The 8-week period with minimal prednisone necessary to confirm CRmin is included as part of this time period. For example, a participant that achieves complete remission with prednisone ≤ 10 mg/day at week 15 for the first time and maintains this status for 8 weeks will have a time to CRmin of $15 + 8 = 23$ weeks.
3. Proportion of participants achieving DC in PV, PF and all participants (composite strategy)
4. Proportion of participants achieving CR in PV, PF and all participants (composite strategy)

For all subsequent secondary endpoints a treatment policy strategy is applied ignoring ICEs.

5. Proportion of treatment failures as assessed by the investigator in PV and in all participants. Specific reasons for treatment failure can be derived as follows in following order:
 - absence of DC: if participant didn't achieve DC as assessed by the investigator
 - prednisone related SAE: occurrence of an SAE after DC considered related to prednisone by the investigator
 - flare: if previous 2 reasons are not applicable, the reason must be a flare between DC and CRmin that is not controlled by a prednisone dose that is 2 dose levels above the dose at which the flare is observed and that is a least 0.3mg/kg qd

Failure is defined for the whole treatment phase.
6. Number of flares in PV and in all participants: count number of flares as assessed by the investigator. A new flare only emerges after a new DC. Number of flares are counted over the whole treatment + follow-up phase, between first DC and CRmin (or end of treatment period for participants without CRmin) and after CRmin. The initial flare at baseline (if applicable) is not counted.

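### SAP 4.1.2 keeps one assessment per window and exempts only time to response, so flare, treatment failure, DC/CR proportions and CRmin duration can omit or late-date events seen at unscheduled visits

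*SAP*

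**What the plan says.** Four pieces of the plan bear on this.

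- **Which visits enter the windows.** SAP 2.2.4: "All assessments, including unscheduled assessments, will be allocated to analysis windows as defined below". Table 3 of that section gives 7-day windows (target day ±3) for Weeks 2 to 29. Week 30 runs from day 208 to the end of the treatment phase, and the first follow-up window covers days 1 to 35. Ties go to the later record.
- **Which record is used.** SAP 4.1.2 opens with "For all references to weeks, analysis visits are considered as described in section 2.2.4 unless specified otherwise" and then gives the rule: "If multiple assessments fall within the same analysis window, only the assessment closest to the target date will be considered unless specified otherwise". It adds: "Other assessments within this window will only be listed and not considered in the below analyses". One exemption follows, introduced by the word *Only*: the time-to-response endpoint of 4.1.2.2, which "will be derived using all possible measurements and not only the one closest to the target of the analysis visit".
- **Where events are expected to appear.** Protocol Section 8, Unscheduled Visits: "In case of suspected new lesions as reported by the participant, AEs, flare, or other safety reasons, participants should come to the clinic". Table 4 there requires PDAI and disease assessment at such visits.
- **How the endpoints are defined.** For the primary endpoint, SAP 4.1.2.1 says: "Any CRmin achieved with a relative day up to day 218 is counted as a primary endpoint response". For flares, SAP 4.1.2.3 says only to "count number of flares as assessed by the investigator" over the treatment and follow-up phases.

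**The concern.** Picking the record nearest the target day suits a score summarised by visit, such as PDAI. It does not suit an event endpoint, where the question is whether and when something happened: a record that is not selected may be the one that holds the event. Flare and loss of remission are what the protocol's unscheduled visits are meant to catch, so the rule acts on the visits most likely to carry these events.

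At stake are the secondary endpoints in SAP 4.1.2.3: number of flares, proportion with flare, time to first flare, treatment failure, proportions achieving DC and CR, and duration of CRmin. Flare rate and treatment-failure rate are named secondary endpoints in Protocol Section 3, and time to first flare is marked as a topline output in SAP 8.1. Coherence is a further issue: time to CR uses every record while the proportion with CR does not, so one participant can be an event in the first and a non-responder in the second.

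**Working it through.** The plan gives no figure to reproduce. The check has two parts: which endpoints the rule reaches, and how often it passes over an unscheduled record.

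**1. Reach, endpoint by endpoint**

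| Endpoint | Governing text | Records used |
|---|---|---|
| CRmin within 30 weeks (primary; PV+PF; PF) | SAP 4.1.2.1, followed by 4.1.2.2 item 1 and 4.1.2.3 item 1 | Any CRmin up to day 218; non-response only if CRmin was never ticked |
| Time to CR, time to DC | Exemption in SAP 4.1.2 | All |
| Time to CRmin | 4.1.2.3 item 2, derived like time to CR | All |
| Week 30 landmark | 4.1.2.1, by analysis visit | Selected record, as intended |
| DC and CR proportions, treatment failure, number of flares, time to first flare, proportion with flare, duration of CRmin | 4.1.2.3 items 3 to 9; no override | Default: closest to target |

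The statements that failures and flares are counted over whole phases set the period. They do not say which records are used. Time to first flare sits in 4.1.2.3, outside an exemption that cites 4.1.2.2.

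**2. Illustrations from the windows**

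- Week 14 has target day 7 × 14 + 1 = 99 and covers days 96 to 102. A planned visit on day 99 without an event and an early-discontinuation visit on day 101 recording treatment failure are 0 and 2 days from target. Day 99 is used. If the participant rolls over to the extension, this trial has no later visit to record the failure.
- With CR recorded on day 101 after a planned day 99 visit without CR, and lost again by day 106, the participant has an event in time to CR but is not counted in the proportion achieving CR.
- The follow-up Week 3 target is day 21. A flare recorded on follow-up day 14 (7 days off) loses to a flare-free visit on day 21 (0 days off).

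**3. How often the unscheduled record is passed over (Weeks 2 to 29)**

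Inputs: planned visit at offset s from −2 to +2 days (Protocol Section 1.3 visit window); unscheduled visit at offset u from −3 to +3 days (SAP Table 3 window), on a different day. The unscheduled record is not selected if |u| > |s|, or if |u| = |s| and u is earlier than s. Assumption: all pairs equally likely.

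| Planned offset s | Not selected, of 6 |
|---|---|
| −2 | 2 (33%) |
| −1 | 4 (67%) |
| 0 | 6 (100%) |
| +1 | 5 (83%) |
| +2 | 3 (50%) |

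Total: (2 + 4 + 6 + 5 + 3) / 30 = 20/30 = 67%.

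This applies when the window also holds a planned disease assessment, as it does during weekly on-site visits. If no other assessment falls in the window, nothing is passed over. With 4-weekly assessments between CR and CRmin, about one window in four holds a planned one, giving about 0.25 × 67% = 17%, and at most 0.25 × 100% = 25%.

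**The case against.** **Scope.** The paragraph begins with references to weeks, and flare and failure are defined without any week, so a programmer could treat them as outside the rule. This does not settle the matter. Time to CR and time to DC are not defined by week either, yet the SAP exempts them and says that only they are exempt; if event endpoints were already outside, that sentence would do nothing. Where the SAP wants every record elsewhere, as for worst-case values in 2.2.5, it says so.

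**Re-recording.** After new lesions or a flare, a participant who was in CR returns to weekly on-site assessment until CR is regained. A new flare is counted only after a new DC, so a flare still present at the next visit is counted once and merely dated about a week late. Under the lesion-count limb of the definition, lesions must persist beyond a week, so they would often be visible at the neighbouring planned visit too. This stands for many flares. It does not cover an event at the last visit before rollover, a flare falling in the 35-day follow-up window, or a CR or DC that does not last.

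**Selection is per parameter.** SAP 2.2.4 removes missing values before selecting. If the eCRF stores a flare only when present, a flare-free visit may hold no competing value. The documents do not show the form, so this stays open.

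**Low stakes.** All affected endpoints are outside the fixed testing sequence of SAP 4.1.4, and the unselected records are still listed. This stands and limits the weight of the point.

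**Two stronger readings do not hold.** A reader might infer that CRmin can be lost from the primary endpoint: with assessments on day 210 and day 217, both in the Week 30 window, and CRmin ticked on day 217, the default rule would use day 210. But the default yields where something else is specified, and 4.1.2.1 specifies it: CRmin counts by relative day up to 218, so this participant is a responder. A reader might also take 67% as the share of flares lost. It is only the chance that one record is not selected.

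**Conclusion.** The point holds for the event endpoints in SAP 4.1.2.3 that have no rule of their own: number of flares, proportion with flare, time to first flare, treatment failure, DC and CR proportions, and duration of CRmin. Taken literally, the SAP can omit or late-date events observed at unscheduled or early-discontinuation visits, and can make the CR or DC proportion disagree with the matching time-to-event count.

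The primary and key secondary CRmin proportions and time to CRmin are not affected. What remains there is a wording mismatch: *Only* in 4.1.2 leaves no room for the exemption that 4.1.2.1 makes.

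The size is known only as a record-selection rate, 67% (33% to 100%), under equally likely days and a planned assessment in the same window. The number of events lost, and any effect on the treatment comparison, cannot be derived from the documents. They depend on how often unscheduled visits occur, how often an event is recorded again, and how the eCRF stores absence of an event.

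**What to change.** In SAP 4.1.2, replace the single exemption with two statements:

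- Investigator-assessed events (CRmin within 30 weeks, CR, DC, flare, treatment failure, loss of CRmin) are derived from all scheduled and unscheduled assessments.
- Closest-to-target selection applies only to by-visit summaries (PDAI, QoL and similar) and to the Week 30 landmark.

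This also brings the word *Only* into line with 4.1.2.1. The cost is a short SAP text change and one derivation change, with no new data collection.
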